**A COMPARISON OF METHODS OF DISCONTINUING NASAL CPAP IN PREMATURE INFANTS <30
WEEKS GESTATION – A FEASIBILITY STUDY**

NCT03292562

Version Date: 09/13/2017

A COMPARISON OF METHODS OF DISCONTINUING NASAL CPAP IN PREMATURE INFANTS <30 WEEKS GESTATION – A FEASIBILITY STUDY

[name]; [name]; [name]

Introduction: Nasal continuous positive airway pressure (NCPAP) mode of respiratory support is now widely used to support premature infants, especially those who are less than 30 weeks of gestation.¹⁻² Recently, three large studies have shown that NCPAP therapy initiated in the delivery room is equally effective as prophylactic surfactant in the treatment of respiratory distress syndrome (RDS).³⁻⁵ Additionally, volutrauma and atelectrauma have been implicated in the development of Bronchopulmonary dysplasia (BPD).⁶ Therefore, premature infants are being preferentially treated with NCPAP rather than mechanical ventilation. However, while there is significant body of literature justifying the use of NCPAP, very little is known about how long to continue CPAP and more importantly how and when to wean off NCPAP. There are three published trials, one of which showed, that infants are likely to tolerate being taken off NCPAP after gradual reduction in pressure with some increase in oxygen need.⁷ The second trial showed, that weaning from NCPAP to supplemental oxygen via high flow nasal cannula (HFNC) did not decrease duration of NCPAP therapy but, increased the duration of oxygen use.⁸ Another recent trial showed, that discontinuation of NCPAP, rather than cycling NCPAP, results in faster weaning off CPAP. In clinical practice, CPAP is either discontinued regardless of the pressure or, the pressure is gradually reduced before discontinuing CPAP based on individual physician preferences. However, a clinical trial comparing discontinuation of NCPAP with and without weaning the CPAP pressure has not been published. Therefore, this is a feasibility study comparing two strategies of discontinuing NCPAP.

Study question:

Among infants <30 weeks gestational age on NCPAP, does discontinuing CPAP after gradual reduction in CPAP pressure leads to successful weaning off CPAP when compared to discontinuing CPAP without weaning pressure.

P: Premature infants <30 weeks gestation requiring NCPAP therapy for respiratory support who are ready to wean NCPAP

I: Wean NCPAP pressure gradually before discontinuing NCPAP

C: Discontinue NCPAP without weaning pressure

O: Number of total days on NCPAP after wean started or discontinuation, failure to wean off NCPAP, time to failure, need for intubation

T: 28 days after randomization

Study Population:

- Inclusion criteria:**

- All infants < 30 weeks by dates, on NCPAP therapy, on caffeine 10mg/kg daily
- Meet CPAP stability criteria for ≥ 12 hours
 - CPAP 6 cm H₂O
 - FiO₂ <= 0.25 and stable (to maintain sats 85-95%)
 - Respiratory rate consistently less than 60
 - Mild to no subcostal/intercostal retractions
 - No Apnea or bradycardia event that requires bag mask ventilation
 - Less than 3 apnea/brady/desat episodes in any 1 hour period for previous 6 hours.
 - Tolerated time off CPAP during routine CPAP care (~15 min)

- **Exclusion criteria:**
 - Major congenital anomalies including congenital heart disease
 - Anomalies that prevent discontinuation of NCPAP
 - Undergoing current evaluation for and/or treatment of sepsis

Allocation Plan: Blinding is not possible due to technological constraints. Subjects will be randomized using permuted blocks using 4-6-6 scheme. Assignment will be sequentially numbered and placed in opaque envelopes. Consent will be obtained in first 48hrs of life in potentially eligible patients. Subjects will be randomized once the subject meets eligibility (CPAP stability) criteria.

Interventions:

1. **Discontinue NCPAP after weaning pressures:** After randomization, CPAP pressure will be weaned by 1 every 24hours as long as the subjects continue to meet stability criteria after each wean, until CPAP of 4. If after decrease in CPAP pressure, the subject meets CPAP failure criteria (described below) pressure will be increased back to the previous level and after stabilization for 24 hours weaning process will be started again. Once the subject meets stability criteria on CPAP of 4, NCPAP will be stopped and subject will be placed on nasal cannula (NC) according to unit guidelines (max 1L flow, 30% FiO₂). Subjects will be considered to have failed CPAP discontinuation if they meet any one of the CPAP failure criteria after routine suctioning and prone positioning:
 - Respiratory rate >75 consistently
 - Respiratory distress defined as moderate-severe retractions, grunting, nasal flaring that persists for >30 min
 - FiO₂ >30% for 6 hours* (to keep oxygen saturations 85-95%)
 - Apnea or bradycardia that requires bag mask ventilation
 - >2 apnea/bradycardia episodes in 1 hourperiod

Subjects will be restarted on CPAP of 6 and will be allowed to recover for 1 week. After 1 week, the weaning procedure will start again if the subject meets CPAP stability criteria.

2. **Discontinue NCPAP without weaning pressures:** After randomization, once the subject meets stability criteria, NCPAP will be stopped and subject will be placed on nasal cannula (NC) according to unit guidelines (max 1L flow, 30% FiO₂). Subjects will be considered to have failed CPAP discontinuation if they meet any one of the CPAP failure criteria as described before. Subjects will be restarted on CPAP of 6 and will be allowed to recover for 1 week. After 1 week, the weaning procedure will start again if the subject meets CPAP stability criteria.

End of study: Each patient will be followed for 28 days from randomization OR failure of CPAP wean x 2 attempts. Should patient need further escalation of care from CPAP, will be eligible to enter NIPPV study.

Outcomes: Primary outcome of interest is the number of days on NCPAP or mechanical ventilation from randomization until discharge (1 day= 0-24h). Secondary outcomes to be analyzed will be duration of endotracheal ventilation, failure to wean off NCPAP, rate of BPD, rate of NEC, time to full PO ad lib feeds, length of hospital stay, rate of air leak disorders.

Sample size calculation: This type of intervention has not been reported in literature as a result we have no prior data to help us determine the sample size. Therefore, this study will carried out in two phases. During the initial phase, the study will be carried out for 1 year. The data from the first phase will be used estimate the sample size for the subsequent definitive trial. The initial goal for enrollment is 50 patients.

Data analysis:

Baseline characteristics to be collected:

- Gestational age
- Birth weight
- Prenatal steroids
- Surfactant use
- Corrected gestational age at enrollment
- Weight at enrollment
- Duration of NCPAP before enrollment
- Duration of mechanical ventilation
- Co morbidities such as NEC, Sepsis episodes, IVH, treatment of PDA

Outcome indicators to be collected

- Total days on NCPAP since enrollment
- Total days on endotracheal ventilation since enrollment
- Time to wean off NCPAP
- Number of attempts
- Total days until full PO feeds
- Length of hospital stay

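### Printing the 4-6-6 block sizes in an open study makes some allocations predictable (26–27% expected to be certain if the order is fixed and known) when entry timing rests partly on judgement

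*Combined protocol and SAP*

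**What the plan says.** Four statements in the Allocation Plan matter here.

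- Openness: "Blinding is not possible due to technological constraints". Whether an infant is weaned in steps or taken straight off CPAP is visible at the bedside, so past assignments can be known.
- Sequence: "Subjects will be randomized using permuted blocks using 4-6-6 scheme".
- Concealment: "Assignment will be sequentially numbered and placed in opaque envelopes".
- Timing: "Consent will be obtained in first 48hrs of life in potentially eligible patients", and later "Subjects will be randomized once the subject meets eligibility (CPAP stability) criteria".

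The stability criteria are listed under Study Population, where an infant must "Meet CPAP stability criteria for ≥ 12 hours". Most are numeric or countable: the CPAP level, the FiO₂ limit, the number of episodes per hour, no event needing bag-mask ventilation, and tolerated time off CPAP. Two rest on judgement: "Respiratory rate consistently less than 60", where the adverb is not defined, and "Mild to no subcostal/intercostal retractions".

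The document does not state the allocation ratio, whether the list is stratified, or whether the order of the block sizes is fixed or random. Nor does it say who prepares the list, who holds and opens the envelopes, who judges stability, or whether bedside staff are kept unaware of the block sizes.

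**The concern.** An opaque envelope hides the card but not the arithmetic. In a permuted block of known size, once one arm has used its places, every remaining assignment in that block is known. Before that point, the arm with more places left is the better bet.

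Consent is taken well before randomization, so the step that remains before the envelope is the declaration that the infant is stable. A person who foresees the next arm could put off that declaration or, within the numeric limits, bring it forward. The Introduction says that present practice follows the preference of individual physicians, so some may favor one arm for a given infant.

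Readiness at randomization bears directly on the primary outcome, days on NCPAP or mechanical ventilation, and on failure to wean. Under Sample size calculation, the data from this phase are to be used to size the definitive trial, so a distorted difference would carry forward.

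**Working it through.** The documents give no predictability figure, so there is none to reproduce.

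**Inputs from the documents.** Block sizes 4, 6 and 6, which make a set of 16 (Allocation Plan); two arms (Introduction); an enrollment goal of 50 (Sample size calculation).

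**Assumptions.** Allocation is 1:1, in one unstratified list, and the observer knows the block sizes and all past assignments.

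**Certain assignments in one block.** In a 1:1 block of size 2m, the expected number of forced assignments at the end is the sum over k = 1 to m of 2·C(2m−k, m)/C(2m, m).

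- Block of 4: 2·3/6 + 2·1/6 = 1 + 0.333 = 1.333 (33.3% of the block).
- Block of 6: 2·10/20 + 2·4/20 + 2·1/20 = 1 + 0.4 + 0.1 = 1.5 (25.0% of the block).

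**Fixed, repeating 4-6-6.** Per set: (1.333 + 1.5 + 1.5)/16 = 4.333/16 = 27.1%. Three sets make 48 infants and 3 × 4.333 = 13 certain assignments. Infants 49 and 50 open a new block of 4, where nothing is yet forced. Over the planned 50 this is 13/50 = 26.0%. In simulated lists of 50, the middle 95% ran from 20% to 34%.

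**Best-guess accuracy.** The expected number of correct guesses in a block is m + (2^(2m)/C(2m, m) − 1)/2.

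- Block of 4: 2 + (16/6 − 1)/2 = 2.833.
- Block of 6: 3 + (64/20 − 1)/2 = 4.1.
- Per set: (2.833 + 4.1 + 4.1)/16 = 11.033/16 = 69.0%, against 50% by chance.

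**Other readings of the order.** These were simulated for lists of 50, with an observer who knows the possible sizes and their probabilities but not the order, and who updates after each assignment.

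| Scheme | Expected certain | Best guess correct |
|---|---|---|
| 4-6-6 fixed and repeating | 26% | 69% |
| 4, 6, 6 shuffled within each set | 16% | 68% |
| 4 or 6 drawn independently, weights 1/3 and 2/3 | 7% | 69% |
| 4 or 6 drawn independently, equal weights | 6% | 69% |
| 2, 4, 6 or 8 drawn independently, equal weights | 2% | 68% |

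Varying the sizes removes most of the certain assignments. It hardly changes best-guess accuracy while the sizes are known.

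**Planned adjustment.** The Statistical analysis plan lists gestational age, birth weight, prenatal steroids, surfactant, and CPAP duration and mechanical ventilation before weaning. A systematic delay would show partly as longer prior CPAP. No listed covariate measures how stable the infant was at randomization.

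**The case against.** The strongest objection is that the printed phrase does not establish a fixed order. It may name only the mix of block sizes, with the order random, and then the certain share is about 16% or about 6–7%. This stands. Naming the 6 twice makes a sequence or a set more natural than free draws, but the text settles neither reading.

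A reader might infer that up to 27% of allocations can be deduced. The documents do not support that. The figure is an expected value under the least favorable reading of the order, not a ceiling. A single set could have as many as 2 + 3 + 3 = 8 of 16 forced, and the expectation for 50 infants is 26%.

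A reader might also infer that the staff who can predict the next arm are those who declare stability. This is plausible in an open study, but no assessor or envelope holder is named.

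The room for discretion is limited as well. Most criteria are numeric and must hold for at least 12 hours, which constrains early declaration more than delay. Consent in the first 48 hours of life largely removes selection at consent. The adjusted analysis would absorb part of any effect of delay. These points reduce the risk but do not remove it.

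Finally, no effect on days of NCPAP has been quantified, and this is a feasibility study of 50 infants. That is fair, and it argues for a modest priority. It does not argue for leaving the block sizes in print.

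**Conclusion.** The weakness is real but conditional. The plan prints its block sizes in an open study and makes the moment of randomization depend partly on judgement. With 1:1 allocation, one list, and staff who know the sizes and past assignments, the expected share of certain allocations runs from about 6% to about 27%, depending on an order that the plan does not state.

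The arms could therefore differ in readiness to come off CPAP. Whether they would depends on who judges stability and who can follow the sequence, and the plan is silent on both. The planned adjustment would correct such a difference only in part. The point deserves a change because the remedy is cheap, not because bias has been shown.

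**What to change.** Remove the block sizes from the protocol and replace that sentence in the Allocation Plan with wording such as:

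> *The allocation list is computer-generated in permuted blocks whose sizes vary at random, by a person not involved in recruitment or care. Block sizes and their order are held in a restricted document. The date and time at which the infant is declared to meet the stability criteria are recorded before the envelope is opened.*

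Also state the allocation ratio, who holds and opens the envelopes, and who judges stability. In the restricted document, sizes drawn at random from 2, 4, 6 and 8 would bring certain allocations to about 2% even for someone who knew those sizes. The protection beyond that comes from withholding the sizes, since best-guess accuracy stays near 68–69% while they are known. Recording the time does not prevent selective timing, but it allows it to be examined.

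The cost is a wording change and a new list, with no extra infants or staff. The downside is a possible small imbalance. With blocks of up to 8, the arms could differ by up to 4 at the end (27 against 23). With a fixed 4-6-6 order they are equal at 48 and can differ by at most 2 at 50.

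### Does the 30% oxygen limit on nasal cannula make the oxygen criterion for failed NCPAP discontinuation unreachable?

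*Combined protocol and SAP*

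**What the plan says.** Under Interventions, items 1 and 2, an infant whose NCPAP is stopped is "placed on nasal cannula (NC) according to unit guidelines (max 1L flow, 30% FiO₂". The wording of this limit is the same in both arms.

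Item 1 then lists five criteria, any one of which means failed discontinuation. The oxygen criterion is FiO₂ ">30% for 6 hours* (to keep oxygen saturations 85-95" per cent. The others concern respiratory rate, respiratory distress, apnea or bradycardia needing bag-mask ventilation, and repeated apnea or bradycardia episodes. Item 2 carries the list over to the arm without weaning: "Subjects will be considered to have failed CPAP discontinuation if they meet any one of the CPAP failure criteria as described before". In item 1 the same list also governs the pressure step-downs while the infant is still on CPAP.

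The consequence of failure is the same in both arms: "Subjects will be restarted on CPAP of 6 and will be allowed to recover for 1 week". The End of study paragraph adds: "Each patient will be followed for 28 days from randomization OR failure of CPAP wean x 2 attempts".

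**The concern.** The limit and the threshold share the figure 30% but lie on opposite sides of it. Taken literally, an infant managed within the limit can never satisfy the oxygen criterion, and an infant who satisfies it has been outside the limit for six hours. The protocol does not say whether FiO₂ may exceed 30% on cannula during those hours. Nor does it say what to record for an infant held at 30% whose saturations are below target and who meets none of the other four criteria.

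A call of failure matters for several outcomes. It restarts CPAP with a week of recovery, which adds to the primary outcome (days on NCPAP or mechanical ventilation). It defines the secondary outcome of failure to wean, enters the number of attempts and the time to failure, and counts towards the two-failure end of follow-up. An infant with one clear failure and one disputed oxygen episode has either finished the study or is still in it, depending on the reading.

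The trial is open ("Blinding is not possible due to technological constraints"), so a bedside call could be influenced by knowledge of the arm. The results also carry forward: "The data from the first phase will be used estimate the sample size for the subsequent definitive trial".

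**Working it through.** No figure in the plan can be reproduced here. The protocol gives no power calculation and no expected failure rate. The check is a comparison of the statements, followed by a conditional estimate of size.

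**The statements side by side**

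- Cannula limit (Interventions 1 and 2): FiO₂ at most 30%.
- Oxygen failure (Interventions 1, applied to arm 2 by cross-reference): FiO₂ above 30% for 6 hours.
- Overlap if the limit is absolute: none.

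**Strict-ceiling reading.** The oxygen criterion cannot be reached on cannula in either arm. In the weaning arm it would still operate during step-downs on CPAP, where the cannula limit does not apply. In the other arm there are no step-downs, so after randomization the criterion would do nothing. Yet item 2 applies the whole list to that arm, specifically to judge discontinuation. This reading therefore empties a listed criterion of meaning.

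**Oxygen-need reading.** Sustained need beyond what the cannula limit allows is the failure. Three features of the text support this:

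1. The criterion is qualified by the saturation target, so FiO₂ means the amount required to hold that target. The stability criterion in the inclusion list (FiO₂ no more than 0.25) is qualified in the same way.
2. A six-hour window makes sense only if FiO₂ can be above 30% for a time before failure is called.
3. Any one criterion is enough, so oxygen need alone is classified as failure.

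On this reading the limit and the threshold share a figure because one marks where the other begins.

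**Text not available.** The limit refers to unit guidelines, which are not part of the document. The asterisk after the six hours points to a note that is not in the available text. Either might settle the point, and neither can be counted as missing from the plan.

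**Size if an oxygen-only failure is never called**

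Inputs: 50 infants (enrollment goal), equal allocation assumed, 7 days of recovery per failure, and an assumed 0 to 3 such infants per arm.

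- Infants per arm: 50 / 2 = 25.
- Failure rate: 1/25 = 4 percentage points per infant; 3/25 = 12 points for three.
- Mean NCPAP days: 7/25 = 0.28 days per infant; 3 × 7/25 = 0.84 days for three.
- If another criterion later triggers the restart, both the failure count and the primary outcome may be unchanged, so each range starts at zero.

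These are shifts within one arm. With equal numbers affected in the two arms and 7 days for each, the difference between arms does not move. If only one arm is affected, the difference moves by the full amount.

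The 7 days is the planned recovery period and not a bound. In the weaning arm a repeat attempt also steps down from 6 to 4. Assuming 24 hours at 5 and 24 hours at 4, that is 7 + 2 = 9 days, and three infants would give 3 × 9/25 = 1.08 days.

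**The case for a change.** The best case for a change is that a maximum ordinarily means a ceiling, so two clinicians could follow the same text and classify the same infant differently, in a trial without blinding. Oxygen need is also foreseeable: the Introduction cites a trial in which coming off NCPAP after gradual pressure reduction was accompanied by some increase in oxygen requirement. Identical wording does not guarantee identical effect, because only the weaning arm also uses the criterion on CPAP. The first phase is meant to inform the size of the definitive trial, and a clarifying sentence would cost almost nothing.

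Part of this stands. The protocol does not explicitly connect the limit to the criterion, and the infant held at 30% with low saturations is not mentioned. The effect could differ between arms if the ceiling were applied strictly.

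The rest depends on that strict reading, which makes a listed criterion unusable in the setting it was written for. It also presumes that neither the unit guidelines nor the note behind the asterisk resolves the matter. Lack of blinding makes any judgement call more exposed, but it does not show that this criterion would be left to judgement when the text already makes it sufficient for failure.

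**Conclusion.** The concern does not call for a change to the plan. The two statements fail to overlap only if 30% is an absolute ceiling. The protocol classifies sustained FiO₂ above 30% as failure in both arms, and its own wording supports a reading under which the limit and the criterion fit together. What remains is a missing connecting sentence, which staff working under the unit guidelines can sensibly supply, in a 50-infant feasibility study.

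The size cannot be calculated, because the documents give no frequency for oxygen-only failure. Entry at FiO₂ no higher than 0.25 may keep it small. The ranges of 0 to 12 percentage points in one arm's failure rate and 0 to 0.84 days in its mean (1.08 in the weaning arm with the repeat step-down) rest on three assumptions: 25 infants per arm, no more than three affected infants in an arm, and failures that are never called on any other criterion.

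This conclusion concerns only whether the text can be read consistently. How the limit and the criterion relate clinically is for the investigators to state, and no view is taken on which limit or threshold is right.

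### The primary outcome counts support days to discharge, but the end-of-study rule stops follow-up at 28 days or two failed weans and the T line says 28 days; the windows contradict each other

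*Combined protocol and SAP*

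**What the plan says.** Three places in the combined protocol and SAP set a time window for the same count.

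- **Outcomes:** "Primary outcome of interest is the number of days on NCPAP or mechanical ventilation from randomization until discharge (1 day= 0-24h".
- **End of study**, immediately before it: "Each patient will be followed for 28 days from randomization OR failure of CPAP wean x 2 attempts".
- **Study question:** "T: 28 days after randomization". The O line there also differs from the primary outcome: "O: Number of total days on NCPAP after wean started or discontinuation". It leaves out ventilator days and starts the clock at a different point.

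The fields listed under Data analysis count NCPAP and ventilator days from enrollment and give no end date. The secondary outcomes include "time to full PO ad lib feeds, length of hospital stay", which need records up to or near discharge.

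On failure, the weaning-arm text under Interventions says "Subjects will be considered to have failed CPAP discontinuation if they meet any one of the CPAP failure criteria". After a failed discontinuation, both arms return to CPAP for one week, and then "After 1 week, the weaning procedure will start again if the subject meets CPAP stability criteria". The Statistical analysis plan names a t-test for continuous variables and survival methods for time to wean. It has no truncation rule for the day count and no censoring rule for an infant whose follow-up ends at a second failure.

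**The concern.** This is the only outcome labelled primary, and two people abstracting data under this plan could record different values for the same infant. One would count to discharge, one to day 28, and one to the second failed wean.

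The last of these is the most troublesome statistically. It ends the count because the infant did badly, so it removes days from infants likely to need the longest support. The cut also falls at different times in the two arms, because each attempt in the weaning arm begins with days of pressure reduction on CPAP. The arm difference could be biased.

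The Sample size calculation section says that first-phase data will size the definitive trial. If that trial used the uncut outcome, a variance estimated from cut counts would be too small.

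**Working it through.** The plan gives no figure to reproduce: 50 is an enrollment goal without a power basis. The contradiction is textual and does not depend on the arithmetic below, which only shows what the choice of window could do.

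**Inputs from the plan.** Recovery after a failed discontinuation is 7 days. The weaning arm goes from a pressure of 6 to 4, by 1 every 24 hours, and then stops.

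**Assumptions (not in the plan).**
- *w*, CPAP days per attempt before stopping: 0 in the no-wean arm; 1.5 to 3 in the weaning arm, base 2.5.
- *t*, days from stopping to failure: 0.5 to 2, base 1.
- *p*, failure risk per discontinuation: constant across attempts, with weekly retries until success.
- Only failed discontinuations count as failures.

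**Step 1: when the earlier limit bites.** The second failure falls on day 2w + 7 + 2t, with 2w + 7 CPAP days counted.
- No-wean: day 8 to 11, with 7 CPAP days counted.
- Weaning: from 3 + 7 + 1 = day 11 to 6 + 7 + 4 = day 17, with 3 + 7 = 10 to 6 + 7 = 13 CPAP days counted.

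These all fall before day 28. In this range the later-limit reading is therefore the same as 28 days for everyone, and the earlier-limit reading is the one that cuts twice-failing infants short.

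**Step 2: mean counted days per arm.**
- To discharge: (w + 7p)/(1 − p).
- Cut at the second failure: w + p(7 + w).
- To day 28 (t = 1): each attempt's CPAP days are added up and the last is cut at day 28. No-wean: 7(p + p² + p³) + 3p⁴. Weaning: 2.5 + 9.5(p + p²) + 3.5p³.

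Worked example, 60% no-wean and 40% weaning:
- To discharge: 5.3/0.6 − 4.2/0.4 = 8.83 − 10.5 = −1.7.
- To day 28: 8.04 − 8.62 = −0.6.
- Cut: (2.5 + 0.4 × 9.5) − 0.6 × 7 = 6.3 − 4.2 = +2.1.

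Difference in days, weaning minus no-wean:

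| Assumed risk, no-wean/weaning | To discharge | 28 days for all | Earlier of 28 days and second failure |
|---|---|---|---|
| 60%/40% | −1.7 | −0.6 | +2.1 |
| 50%/30% | −0.4 | 0.0 | +1.85 |
| 30%/15% | +1.2 | +1.2 | +1.8 |
| 20%/10% | +1.8 | +1.8 | +2.05 |

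Varying w from 1.5 to 3, the 60%/40% row runs from −3.3 to −0.8 to discharge against +0.7 to +2.8 cut. The 30%/15% row runs from 0.0 to +1.8 against +0.7 to +2.4.

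**Step 3: equal risks.** The shift (cut minus to-discharge) is −p²w/(1 − p). With w = 2.5 it is −0.03 day at 10%, −0.1 at 20%, −0.3 at 30% and −1.25 at 50%.

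**Step 4: direction.** Suppose that twice-failing infants stay on CPAP to day 28 and days are counted to day 28. At equal 50% risk the means are then 2.5 + 0.5 × 9.5 + 0.25 × 14 = 10.75 and 3.5 + 0.25 × 19 = 8.25, a difference of +2.5. The cut difference is 7.25 − 3.5 = +3.75, so the shift is +1.25. The bias can take either sign.

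**Step 5: how many infants.** Expected double failures per 25 infants are 25p²: 1.0 at 20%, 2.3 at 30% and 6.3 at 50%.

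**The case against.** The best defence is that End of study closes only protocol-directed weaning and that outcomes are read from the chart to discharge. The Outcomes sentence names discharge outright, length of stay and full oral feeds need late records, the NCPAP field has no end date, and the end-of-study paragraph goes straight on to eligibility for another study. On that reading nothing is cut. This is plausible, and it limits the point to wording. It does not remove it: the sentence says that each patient is followed to that limit, and no passage says that support days are collected afterwards.

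The defence is also right that the T-line mismatch alone has almost no effect in the model at 30%/15% or 20%/10%, and that every risk is assumed.

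A reader might infer two further faults that the documents do not support.

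- **Failed pressure steps count toward the two failures, so weaning-arm infants would leave first.** This is the weaker reading. The no-wean arm has no pressure steps, yet its text also speaks of restarting the weaning procedure after a failed discontinuation, so the term covers a whole attempt. A failed step is handled within an attempt: "If after decrease in CPAP pressure, the subject meets CPAP failure criteria (described below) pressure will be increased back to the previous level". The weaning-arm text does speak of starting the weaning process again after a failed step, so the definition still needs stating.
- **The open-ended retry instruction conflicts with the two-failure limit.** It does not. The end-of-study rule is simply the exit from the retry loop, and the number of attempts remains a usable field.

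**Conclusion.** The point holds as an internal contradiction in the window of the primary outcome. It should be corrected before data are abstracted.

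The consequence is conditional. It arises if the end-of-study rule governs data collection, and chiefly if the earlier limit applies. About 7 counted CPAP days in the no-wean arm against 10 to 13 in the weaning arm for a twice-failing infant then rests on the assumed timings. The effect on the arm difference is unknown, because no failure risks are given. In the model it is a few tenths of a day at low or equal risks (10% to 30%). The sign changes in the base case only at high, unequal risks (50%/30% and above). There is no shift if charts are read to discharge.

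A reader might infer that the primary outcome cannot be measured, or that its result will be reversed. The documents support neither, since collection to discharge is a plausible intention. A reader might also infer that the definitive trial would be undersized by a calculable factor. That needs the definitive trial to use a different window, which nothing in the plan suggests, and a between-infant spread that the plan does not give. Only the direction can be stated: cut counts would understate the variability of uncut ones.

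**What to change.** State one common window for the primary outcome, and align the End of study sentence, the T and O lines and the Data analysis fields with it.

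- **Least change:** say that the end-of-study rule closes only the protocolized weaning phase, and that NCPAP and ventilator days are collected from randomization to discharge for every randomized infant, regardless of failed attempts.
- **Alternative:** a 28-day window for all infants, with the Outcomes sentence changed to match and collection continuing to day 28 after a second failure.

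In either case, say whether the two limits mean the earlier or the later, and how infants who die or transfer before the window ends are counted. In the time-to-wean analysis, do not censor at the second failure: use the actual wean date, or censor at the end of the common window. The sponsor should also reconcile what counts as a failed wean; this review does not choose that rule.

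The cost is protocol wording and, for the discharge window, some extra chart abstraction. Length of stay is already collected. No patients or procedures are added.
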